Evaluation of Triathlon
- a new total knee prosthesis system

[name], ass Prof

Department of Orthopaedics

Lund University Hospital

Dept Orthopaedics Hässleholm Hospital

29 August 2007, Region Skåne, Sweden

NCT02522728

EVALUATION OF THE TRIATHLON KNEE SYSTEM

STUDY DESIGN SUMMARY PAGE

- Prospective, comparative, **randomised**, RSA series with 2-years follow-up.
- Primary total knee replacement surgery utilising the Triathlon Knee System
- A total of 300 patients will be included in the study, with 25 patients in each group of the sub studies.
- Clinical evaluations will be required pre-operatively, per-operatively, prior to discharge and at 3 months +/-2 weeks, 1 year +/- 2 months and 2 years +/- 2 months.
- RSA (Roentgen Stereophotogrammetric Analysis) evaluation will be required prior to discharge and at 3 months +/-2weeks, 1 year +/- 2 months and 2 years +/- 2months.
- Radiographic evaluation will be required to be completed pre-operatively, prior to discharge and at 1 year +/- 2 months and 2 years +/- 2months.
- Patient outcomes assessments (KOOS and KSS) will be required to be completed pre-operatively and at 3 months +/-2 weeks, 1 year +/- 2 months and 2 years +/- 2 months

Evaluation	Pre-op	Per-op	Prior to Discharge	3 Months	1 Year	2 Years
Medical History	✓					
Operative Details		✓				
RSA			✓	✓	✓	✓
Radiographs	✓		✓		✓	✓
Clinical	✓	✓	✓	✓	✓	✓
Outcomes	✓			✓	✓	✓

1. Introduction

Total Knee Arthroplasty (TKA) is the surgical reconstruction of the knee joint in order to relieve pain, restore function and correct deformity. It is a very common surgical procedure with figures showing more than 500.000 arthroplasties performed annually world wide. Total knee arthroplasty is considered one of the most successful types of joint reconstruction in that surgical results usually meet and even exceed expectations.

Efforts to improve the outcome of total knee replacement continue today, with issues such as implant design, material biocompatibility, wear resistance and instrument design being actively researched and refined. The role of implant design is particularly well documented in the literature. The patient's demands and the refinement of surgery have increased the demands, both on the implants and development of the surgical technique.

This clinical study proposes to evaluate a new knee prosthesis system, Triathlon.

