This is a prospective, comparative, randomised single centre clinical study. The Triathlon and the Duracon Knee Systems have to be implanted for evaluation in this study. Patients will be randomised to one of two equally sized groups within each sub study. Both knee systems are commercially available. Patellae will be resurfaced if needed. All patients included in the study will meet all inclusion criterias and none of the exclusion criterias.

Ethic Committee approval for the study will be obtained by the investigator prior to starting the inclusion of patients in the study.

Patients will be considered for enrolment according to the clinical findings and subject to gaining their suitable written informed consent (see Appendix II).

The principal evaluation parameter will be the RSA. Patient outcome will be assessed by the KOOS questionnaire and the KSS. Clinical evaluation will include the chair raise test, measurement of the extension strength, and a patella evaluation. The evaluation of the Triathlon system will be carried out in several steps, described as sub-studies all including RSA-technique.

Sub-studies:

a) Triathlon versus Duracon: The Triathlon system has a heritage in the well documented Duracon system, which has shown very good results in the Swedish Knee Register. The goal with this study is to get an indication of the long-term results of Triathlon. The evaluation is carried out by a prospective randomised RSA-study with Triathlon cemented knee prosthesis versus Duracon cemented knee prosthesis

b) Triathlon Cruciate Retaining (CR) versus Triathlon Posterior Stabilized (PS): During knee prosthesis surgery the surgeon many times need to make a judgement on if to keep a defect anatomical structure or if to replace it with knee prosthesis with a design that allows for adjustment of this defect. This sub study is aimed to evaluate which prosthetic choice to be made in respect of stability, long-term results and patient outcome.

c) Triathlon PA (HA-surface) versus Triathlon Pressfit design: The goal with the uncemented technique is to reach a full integration between the bone and the prosthesis. During the last years the usage of prosthesis with hydroxyapatite surface within tooth-, mandibular-surgery, hips- and knee-joints, have increased significantly. It has been shown that a thin layer of hydroxyapatite stimulates the anchorage of the implant. The

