11.2 Statistical analysis

All variable are considered continuous and measured on an interval scale, except migratory pattern, which is proportional. The difference between the two treatment groups will be evaluated with analysis of variance (ANOVA) for continuous variables at different time periods. Clinical scores will also be analysed using the analysis of covariance (ANCOVA) to compensate for different preoperative starting values. Continuous data which are not normally distributed will be analysed by non-parametric ranking tests and proportional values will be analysed by the chi-square test or the Fischer's exact test at low response frequencies.

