12.3 Ethical committee

The study protocol will be subjected to and approved by the ethical committee of the Medical Faculty, Lund University, before the start of the study.

Amendment No. 2 to Evaluation of Triathlon - a new total knee prosthesis system

3. Number of Subjects

360 patients in six individually randomized sub-studies (30 patients in each randomized group) will be enrolled into the study over a 12 months recruitment period per sub-study.

Study Design Summary Page

- A total of 360 patients will be included in the study, with 30 patients in each group of sub-studies.

**PROTOCOL TITLE:
EVALUATION OF THE TRIATHLON KNEE SYSTEM**

**Protocol addendum - Extended follow-up period with 5, 7 and 10 years
follow-up visits**

Protocol #: K-S-015
Revision: v1.0
Date: 07 May 2014

[figure not shown]
Study responsible doctor

[name]
Dept, Orthop, Hässleholm Hospital
[contact]
e-mail:[contact]

Approved by:

[name]
Clinical Research Director Europe
Stryker SA
[contact]
e-mail: [contact]

Signature: _____

Introduction

The results of knee replacement surgery have continuously improved and operations are now highly cost effective from a social point of view and in terms of improved quality of life for the individual patient. However complications occur, especially in the long term as prosthetic loosening, wear, and infection. Extensive research is on-going to find improved prosthetic materials, better prosthetic design and surgical methods to manage these difficulties.

Adequate surgical expertise and the design of the artificial knee joint are among the most important factors in terms of outcome and long-term results. To evaluate these aspects for the Triathlon prosthesis, it is necessary to collect and analyse data from patients receiving this type of knee prosthesis. By collecting patient information, we can further evaluate some of the overall benefits of modern knee surgery, such as shorter rehabilitation time, generally faster recovery, more natural knee function and improved long-term outcomes. The Triathlon knee system is a further development of both the prosthesis and instrument design. The knee prosthesis design is better adapted to the wide variation of patient anatomy and size.

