Secondary objective

To compare operative time, number of hospital days, blood loss, KSS results, KOOS (questionnaire about symptoms and activity level), EQ-5D (questionnaire about quality of life) unexpected events, radiographs / including RSA.

Extended evaluation schedule

Evaluation	Pre-op	Per-op	PTD	3 Months	1 Year	2 Years	5 Years	7 Years	10 Years
Medical History	X								
Operative Details		X							
RSA			X	X	X	X	X	X	X
Radiographs	X		X		X	X	X	X	X
Clinical	X	X	X	X	X	X	X	X	X
Outcomes (KSS, KOOS, EQ-5D)	X			X	X	X	X	X	X

- RSA (Roentgen Stereophotogrammetric Analysis) evaluation will be required prior to discharge and at 3 months +/- 2 weeks, 1 year +/- 2 months, 2 years +/- 2 months, 5 years +/- 2 months, 7 years +/- 2 months and 10 years +/- 2 months.
- Radiographic evaluation will be required to be completed pre-operatively, prior to discharge and at 1 year +/- 2 months, 2 years +/- 2 months, 5 years +/- 2 months, 7 years +/- 2 months and 10 years +/- 2 months.
- Clinical evaluations will be required pre-operatively, per-operatively, prior to discharge and at 3 months +/- 2 weeks, 1 year +/- 2 months, 2 years +/- 2 months, 5 years +/- 2 months, 7 years +/- 2 months and 10 years +/- 2 months.
- Patient outcomes assessments (KOOS, EQ-5D and KSS) will be required to be completed preoperatively and at 3 months +/- 2 weeks, 1 year +/- 2 months, 2 years +/- 2 months, 5 years +/- 2 months, 7 years +/- 2 months and 10 years +/- 2 months.

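### RSA migration is compared by ANOVA at different time periods with no longitudinal model, so a knee without a 2-year RSA adds nothing to the 2-year comparison although its earlier RSA was measured

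*Combined protocol and SAP*

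**What the plan says.** Section 5 makes RSA the main measure: "The principal evaluation parameter will be the RSA". The study design summary page sets the RSA visits: "RSA (Roentgen Stereophotogrammetric Analysis) evaluation will be required prior to discharge and at 3 months +/-2weeks, 1 year +/- 2 months and 2 years +/- 2months". The 2014 addendum adds RSA at "5 years +/- 2 months, 7 years +/- 2 months and 10 years +/- 2 months" but no analysis.

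Section 11.2 states the comparison: "The difference between the two treatment groups will be evaluated with analysis of variance (ANOVA) for continuous variables at different time periods". Its fallback is "Continuous data which are not normally distributed will be analysed by non-parametric ranking tests". Baseline adjustment is named for the scores only: "Clinical scores will also be analysed using the analysis of covariance (ANCOVA) to compensate for different preoperative starting values". Migratory pattern, a proportion, goes to a chi-square or exact test.

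Amendment No. 2 raises each group from 25 to 30: "360 patients in six individually randomized sub-studies (30 patients in each randomized group) will be enrolled". It gives no reason, so the increase cannot be read as a stated attrition allowance. The documents give no repeated-measures model, imputation rule, analysis set, or rule for a withdrawn patient or missed visit.

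The 2-year contrast is not named as the main comparison. That is inferred from section 11.1, which powers on migration over the first two years, and from the two-year study period.

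**The concern.** A group comparison at 2 years can use only knees with a 2-year value. A patient who stops attending after 1 year has two follow-up RSA results on the same knee, and nothing in section 11.2 brings them in. The rank tests have the same gap. Reading the sentence as classical repeated-measures ANOVA does not help, because that method drops incomplete patients listwise.

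Two things are at stake. One is precision, since data already collected go unused. The other is bias: if knees that migrate more by 1 year are more often lost, the worse arm loses more of its high values and the difference shrinks. Shrinkage is not a safe error everywhere. Sub-study g asks whether the short keel matches the standard keel in fixation and migration, and there a shrunken true difference favours the conclusion of equality.

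**Working it through.** **Inputs from the plan.** SD 0.5 mm, difference 0.5 mm (1.0 against 0.5), alpha 0.05, power 80% (section 11.1); 30 per arm (Amendment No. 2).

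**Assumed, because the documents give no figure.** Loss at 2 years: 10 to 30%, centred on 17% (30 falling to 25). Correlation between 1-year and 2-year migration: ρ = 0.5 to 0.9. Dependence of loss on migration: log-odds of 2 to 4 per mm. The pre-discharge RSA is taken as the migration reference.

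**1. The plan's sample sizes.** The normal formula gives 2 × (1.96 + 0.84)² × (0.5/0.5)² = 15.7, so 16. The t-test gives 16.7, so 17 as stated. The 25 per group for continuous migration (50% against 10%) reproduces with a continuity correction. The sample size is not at fault.

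**2. Precision under random loss.** For n per arm, loss d and SD s, the variance of an arm's 2-year mean is

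- visit-wise: s²/[n(1−d)]
- joint model using the 1-year value: (s²/n) × [1 + (d/(1−d)) × (1−ρ²)]

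With n = 30 and d = 1/6, d/(1−d) = 0.2. The SE of the difference without loss is √(2 × 0.25/30) = 0.129 mm.

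| Analysis | Variance factor | SE (mm) | Effective n per arm |
|---|---|---|---|
| Visit-wise | 1.200 | 0.141 | 25.0 |
| Joint, ρ = 0.5 | 1.150 | 0.138 | 26.1 |
| Joint, ρ = 0.8 | 1.072 | 0.134 | 28.0 |
| Joint, ρ = 0.9 | 1.038 | 0.132 | 28.9 |

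At ρ = 0.8 the variance ratio is 1.072/1.200 = 0.89. For other losses, effective n per arm is:

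| Loss | Visit-wise | Joint, ρ = 0.5 to 0.9 |
|---|---|---|
| 10% | 27.0 | 27.7 to 29.4 |
| 20% | 24.0 | 25.3 to 28.6 |
| 30% | 21.0 | 22.7 to 27.7 |

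**3. Power of the visit-wise test.** For 0.5 mm with SD 0.5 mm, the two-sided t-test has 93% power at 25 per arm (17% loss) and 89% at 21 per arm (30% loss).

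**4. Bias when loss follows observed 1-year migration.** These are simulated normal 1-year and 2-year values with logistic loss after 1 year and a true 2-year difference of 0.50 mm.

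- Random loss: both analyses return 0.50 mm.
- ρ = 0.8, 1-year difference 0.4 mm: visit-wise about 0.46 to 0.47 mm at log-odds 2 per mm and 0.43 to 0.45 mm at 3 per mm; joint model about 0.50 mm. At 17% average loss the visit-wise values are about 0.47 and 0.45 mm; the 0.43 mm end needs loss nearer 25%.
- Wider grid (10 to 20% loss, log-odds 2 to 4 per mm, ρ = 0.5 to 0.9, 1-year means 90% of 2-year means): visit-wise 0.41 to 0.48 mm; joint model about 0.50 mm. At 20% average loss and 2 per mm, 26% are lost in the worse arm and 14% in the better.
- No true difference and the same loss mechanism in both arms: no bias.

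**5. Bias when loss follows the unobserved 2-year value.** On the wider grid, visit-wise gives 0.38 to 0.47 mm and the joint model 0.41 to 0.49 mm. The model is closer to the truth but does not remove the bias.

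**6. Continuous migration from year 1 to year 2.** This proportion needs RSA at both visits. A knee without a 2-year RSA has no value for it, and a model of mean migration does not supply one.

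**The case against.** The strongest reply is that little is lost. Section 11.1 needs 17 knees per group for the mean comparison and Amendment No. 2 plans 30, so substantial loss leaves power for the planned effect above 80%. At 17% loss and ρ = 0.8 the gain is about three knees per arm, and that correlation is an assumption. Comparing groups visit by visit is valid when loss is unrelated to outcome, and nothing in the documents links withdrawal to migration. Even at 25 per arm with the effect shrunk to 0.43 mm, power is about 85%. All of this stands, and it keeps the point from being a threat to the design.

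It does not remove the point. The visit-wise method is right only if loss is unrelated to migration, and the plan has no way to use the earlier RSA if it is not.

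A reader might infer three stronger things that the documents do not support:

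- That the plan says incomplete patients are dropped. It does not; this follows from the method.
- That the result will be biased. This depends on how loss arises, and random loss produces none.
- That a repeated-measures model cures the problem. It does so only if loss is explained by observed values.

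**Conclusion.** The point holds as a cheap improvement. Section 11.2 leaves measured RSA out of the 2-year comparison for any knee without a 2-year value. The cost in precision is small: SE 0.141 mm against 0.132 to 0.138 mm at an assumed 17% loss and ρ of 0.5 to 0.9. The larger concern is conditional bias towards no difference, about 0.03 to 0.07 mm of the planned 0.5 mm if loss follows 1-year migration at log-odds 2 to 3 per mm. The loss rate, correlation and slopes are all assumed, and that 2 years is the main time point is an inference. The documents do not support calling the trial underpowered or its result biased.

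**What to change.** **RSA migration.** In each sub-study, make the primary analysis a likelihood-based repeated-measures model of all scheduled follow-up visits, with group, visit and group-by-visit terms and an unstructured within-patient covariance. Include every patient with a reference RSA and at least one follow-up RSA, and read the 2-year contrast from the model. State in advance that MTPM is log-transformed if skewed; a mean of 0.5 mm with an SD of 0.5 mm, for a quantity that cannot be negative, makes skew likely. A knee without the reference RSA has no migration value, and no model recovers it.

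**KOOS and KSS.** Use the same model, but keep the adjustment that section 11.2 already plans by entering the preoperative score as a covariate.

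**Missing data.** Report withdrawals and missed visits by arm with reasons. Add one missing-not-at-random sensitivity analysis that covers both mean migration and the year-1-to-2 continuous-migration proportion, since the model does not address the latter.

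**Cost.** SAP wording and some programming; no new visits or data. The model assumes loss is explained by observed values, which is weaker than what the visit-wise ANOVA needs. For RSA on the same scale, with no data missing, its 2-year contrast equals the simple group difference, so little is given up if loss proves small.

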8.5 Follow-up

The study period will be two years. Follow-ups will be performed at postoperatively, at 12 weeks and at 1- and 2 years. All assessment variables will be compiled preoperatively and at each follow-up. The patients will be followed indefinitely at 3 years intervals after completion of this protocol.

9. Assessment

Primary assessment variables will be

1. Roentgen stereophotogrammetric analysis (RSA) (Selvik, 1974).

Secondary assessment variables will be

2. Plain radiographs will be obtained for disease classification.
3. Clinical assessment according to the Knee Society Score (KSS) and KOOS score
4. At the post-op follow-up all plain radiographs will be obtained for the assessment of the component position. At the yearly radiographic follow up a weight-bearing investigation will be performed to assess wear, radiolucent zones and stress resorption. A patella sky view projection will be included in the postoperative x-ray and at the yearly controls

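### Section 11.2 extends baseline adjustment only to undefined clinical scores, so extension strength (and the chair raise test, if numeric) is left, read literally, without a baseline term and loses some precision

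*Combined protocol and SAP*

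**What the plan says.** Section 11.2 treats nearly everything as continuous: "All variable are considered continuous and measured on an interval scale, except migratory pattern, which is proportional". The default comparison carries no baseline term: "The difference between the two treatment groups will be evaluated with analysis of variance (ANOVA) for continuous variables at different time periods". The alternative for skewed data carries none either: "Continuous data which are not normally distributed will be analysed by non-parametric ranking tests". Baseline adjustment enters in one sentence only: "Clinical scores will also be analysed using the analysis of covariance (ANCOVA) to compensate for different preoperative starting values".

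The two measures at issue appear in section 5: "Clinical evaluation will include the chair raise test, measurement of the extension strength, and a patella evaluation". On timing, the Study Design Summary Page says: "Clinical evaluations will be required pre-operatively, per-operatively, prior to discharge and at 3 months +/-2 weeks, 1 year +/- 2 months", and it continues to 2 years. The 2014 addendum keeps the pre-operative clinical visit and extends follow-up to 10 years. Section 8.5 adds: "All assessment variables will be compiled preoperatively and at each follow-up".

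Section 9 lists the assessment variables as RSA, radiographs, KSS and KOOS. Extension strength and the chair raise test are not on that list, and no passage assigns either of them an analysis by name.

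**The concern.** The plan gives its own reason for ANCOVA on the scores: patients start from different levels before surgery. The same reason applies to muscle strength, and the plan offers no ground for treating it differently. Strength is a measured quantity rather than a score, so on an ordinary reading the ANCOVA sentence does not reach it.

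With 25 or 30 patients per group, chance differences at baseline are common. If pre-operative strength predicts later strength, an unadjusted comparison has a wider interval than the data require, and the observed difference carries part of any chance imbalance. Because the scope of *clinical scores* is open, the choice between adjusted and unadjusted models for these two measures could also be made after the results are seen. Sub-studies e and f ask whether the patient gains an advantage, and functional measures bear on that question.

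**Working it through.** **1. The plan's own sample sizes (section 11.1).**
- MTPM 1.0 v 0.5 mm, SD 0.5, two-sided alpha 0.05, power 80%. Normal approximation: n = 2 × (1.960 + 0.842)² × (0.5/0.5)² = 15.7, so 16. Exact noncentral t: 17 per group (power 80.7%). The plan's 17 is reproduced.
- Continuous migration 50% v 10%: 20 per group without and 25 with continuity correction. The plan's 25 is reproduced.

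Both rest on RSA, so nothing below changes them.

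**2. Inputs.** Group size is 25 (section 3) or 30 (Amendment No. 2). The documents give no SD, target difference or correlation for strength or chair raise. Differences are therefore in SD units, a 0.5 SD difference is used for illustration, and r is assumed over 0 to 0.7.

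**3. Formulas.**
- Variance of the ANCOVA treatment difference relative to ANOVA: f = (1 − r²) × [1 + 1/(2n − 4)]. The second factor is the expected cost of estimating the slope.
- Power: two-sided 5% noncentral t with effect 0.5/√f and noncentrality (0.5/√f) × √(n/2). Error degrees of freedom are 2n − 3 for ANCOVA and 2n − 2 for ANOVA (where f = 1).

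Example, n = 25 and r = 0.5: f = 0.75 × (1 + 1/46) = 0.766; effect 0.5/√0.766 = 0.571 SD; power 50.7%.

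**4. Results.**

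| Assumed r | Variance change, n = 25 | Power, n = 25 | Power, n = 30 |
|---|---|---|---|
| Unadjusted | – | 41.0% | 47.8% |
| 0 | +2% | 40.3% | 47.1% |
| 0.3 | −7% | 43.5% | 50.7% |
| 0.4 | −14% | 46.4% | 53.9% |
| 0.5 | −23% | 50.7% | 58.7% |
| 0.7 | −48% | 67.0% | 75.2% |

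**5. Break-even.** Setting f = 1 gives r² = 1 − 1/[1 + 1/(2n − 4)]. This is r = 0.15 at n = 25 and r = 0.13 at n = 30.

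**6. Chance imbalance.** The difference in baseline means has standard error √(2/n), which is 0.283 SD at n = 25. By the normal approximation it reaches 0.25 SD or more in either direction in about 38% of trials (33% at n = 30). At r = 0.5, a 0.25 SD imbalance moves the expected unadjusted difference by 0.5 × 0.25 = 0.125 SD in that sample.

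**The case against.** Several stronger readings are tempting, and the documents do not support them.

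- **The plan confines these tests to unadjusted ANOVA.** A reader might infer this, but *clinical scores* is undefined, and the stated purpose of the ANCOVA sentence could cover any clinical measure with a pre-operative value. Non-normal data go to rank tests, not ANOVA. What stands is the literal reading and the lack of a named analysis.
- **Both tests are certainly measured before surgery.** This is the natural reading but is not stated for each test. The same clinical row is ticked per-operatively, when a chair raise test cannot be done, so a tick does not mean that every component is done at that visit. The section 8.5 sentence does not settle it: the section 9 list omits both tests, and the sentence cannot be literal for RSA, which starts before discharge.
- **The unadjusted comparison is biased.** It is not. Allocation is randomised, so ANOVA is unbiased over randomisation. The issue is efficiency, together with imbalance in the one sample obtained.
- **These are key outcomes.** RSA is the principal parameter. Section 9, the addendum's assessment list and its secondary objective all omit both tests.

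Two further objections limit the size and scope. The gain depends on a correlation the documents do not give, and below about r = 0.15 there is none. The scale of the chair raise test is not described, so ordinary ANCOVA may not suit it. Both are fair. The answer to the first is that the possible loss is about 2% of variance, against a gain of 14% to 48% at r of 0.4 to 0.7.

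**Conclusion.** The point holds as a gap in scope with a modest cost in precision. The plan accepts baseline adjustment for scores and, read literally, does not carry it to extension strength or to a numeric chair raise test. For a 0.5 SD difference the gain in power from adjusting at 25 per group is about 5 points at r = 0.4, 10 at r = 0.5 and 26 at r = 0.7; at 30 per group it is about 6, 11 and 27. It is slightly negative at r = 0.

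This rests on three assumptions: that both tests are recorded pre-operatively, that r lies clearly above 0.15, and that the measures are roughly continuous. No conclusion on RSA or on a listed secondary variable depends on it. It is worth correcting because the correction is nearly free and settles the model before the results are seen.

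**What to change.** Keep the existing ANCOVA sentence in section 11.2, so that KSS and KOOS stay covered, and add after it:

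*Extension strength, and the chair raise test where recorded as a number, will likewise be analysed by ANCOVA with the pre-operative value as covariate, as the main between-group analysis; if residuals are clearly non-normal, a rank-based ANCOVA will be used.*

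The addition should not replace the current sentence, since that would drop ANCOVA for the two listed scores. It should also not make ordinary ANCOVA the only permitted test, since that would remove the plan's provision for non-normal data.

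Confirm in section 5 or in the evaluation schedule that both tests are recorded pre-operatively, and state how the chair raise test is scored. The cost is one or two sentences, with no new data if the pre-operative values are already collected. The downside is one degree of freedom and about 2% more variance if the baseline proves uninformative.
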